Official title: Synergistic effect of ^{18}F -FDG PET radiomics and International Prognostic Index on outcome prediction in diffuse large B-cell lymphoma

NCT number: 04317313

Document date: July 29, 2021

Study Protocol and Statistical Analysis Plan

Background: Previous studies have shown that ¹⁸F-FDG PET radiomics is predictive of survival in DLBCL. However, to the best of the investigator's knowledge, a multi-feature radiomic signature for prognosis assessment of DLBCL has not yet been described. Furthermore, it remains unclear whether PET-based radiomics could add more prognostic values to the IPI in DLBCL.

Objectives: This study aims to develop ¹⁸F-FDG PET radiomic signatures, and investigate whether the RS could improve the prognostic value of the IPI in predicting progression-free survival (PFS) and overall survival (OS) in DLBCL.

Study design and methods:

Study population

We retrospectively included patients with newly-diagnosed DLBCL between July 2013 and July 2019 in our institution. The inclusion criteria were: 1) histopathologically confirmed DLBCL, 2) over 18 years old, 3) underwent pre-treatment ¹⁸F-FDG PET/CT, and 4) initial treatment with R-CHOP (rituximab, cyclophosphamide, doxorubicin, vincristine, and prednisone) or R-EPOCH (rituximab, etoposide, prednisone, vincristine, cyclophosphamide, and doxorubicin). Patients were excluded if they had coexistent central nervous system lymphoma or second primary cancer, underwent surgical resection, or had an incomplete follow-up.

Clinical variables including gender, age at diagnosis, cell of origin, performance status, B symptoms, Ann Arbor stage, serum lactate dehydrogenase level, serum β 2-microglobulin (β 2-MG) level, extranodal involvement and treatment regimens of each patient were recorded. The IPI score was calculated.

Patient Treatment and Follow-up

Patients were initially treated with standard first-line chemotherapy every 21 days. Response to treatment was assessed according to the Lugano classification.

Follow-up was performed every 3 months after the completion of treatment, and ended in July 2021. The endpoints included OS (defined as the period from the initial diagnosis to the death from any cause) and PFS (defined as the period from the initial diagnosis to the progression, relapse or death from any cause).

PET Image Segmentation and Feature Extraction

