PET images were analyzed by two experienced nuclear medicine physicians who were blind to the patients' outcome. The volumes of interest (VOIs) were semiautomatically delineated using the LIFEx software (<https://www.lifexsoft.org/index.php>) with a fixed threshold of 41% SUVmax. A total of 1245 radiomic features were extracted via PyRadiomics software. The radiomics features consisted of four groups: (1) first-order statistics features; (2) shape descriptors features; (3) texture features calculated by gray level co-occurrence matrix (GLCM), gray level dependence matrix (GLDM), gray level run length matrix (GLRLM), and gray level size zone matrix (GLSZM); (4) filter and wavelet features obtained by filter and wavelet transformation of the original image, such as exponential, logarithm, square, square root and eight frequency band combinations (low-high-low [LHL], low-high-high [LHH], high-low-low [HLL], low-low-high [LLH], high-low-high [HLH], high-high-high [HHH], high-high-low [HHL] and low-low-low [LLL]).

Radiomics feature selection

First, intra-class correlation coefficients (ICCs) were used to evaluate the inter- and intra-observer agreement for 1248 features, including 3 conventional and 1245 radiomics features. Features with both inter- and intra-observer ICCs greater than 0.75 were retained. Then, the least absolute shrinkage and selection operator (LASSO) Cox regression algorithm with 10-fold cross-validation was applied to select the optimal features with non-zero coefficients in the training set. The radiomics signature was developed by linear combination of the selected features weighted by their respective coefficients. The cut-off value of the radiomics signature was identified by X-tile software. Based on the cut-off value of the R-signature, patients were divided into high-

and low-risk groups. Survival function of the R-signature was estimated by Kaplan-Meier analysis, and survival distributions were compared using log-rank test.

Model construction

Univariate Cox regression analysis was performed to investigate the prognostic value of the R-signature and clinical variables. Then, all significant variables were enrolled into a stepwise multivariate Cox regression to build an integrated radiomics-based model for PFS and OS prediction.

Model performance assessment

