Time-dependent ROC curve analysis was conducted to investigate the predictive accuracy of the R-signature, clinical variables and the integrated radiomics-based model. The 95% confidence interval (CI) of the area under the curves (AUCs) were calculated by bootstrapping with 1000 resampling. The AUC between the radiomics-based model and clinical variables was compared by using the Delong's test. The calibration plots and the Hosmer-Lemeshow test were used to compare the predicted and observed probabilities of the radiomics-based model. The decision curve analysis (DCA) was applied to determine the clinical utility by quantifying the net benefits under different threshold probabilities in the whole cohort.

Statistical analysis

The chi-square test and independent *t*-test were performed using SPSS software (version 25.0, IBM). ICC, LASSO regression analysis, time-dependent ROC analysis, Delong's test, calibration plots, Hosmer-Lemeshow test, DCA and Kaplan-Meier survival analysis were performed using R software (version 3.6.1, <http://www.r-project.org>). A two-sided *P* value of < 0.05 was considered statistically significant.

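### Calibration of a Cox model for censored PFS and OS is tested by Hosmer-Lemeshow with no horizon or censoring rule; beyond about 2 years the P value would depend on how censored patients are coded

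*Combined protocol and SAP*

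**What the plan says.** Under Model construction: "Then, all significant variables were enrolled into a stepwise multivariate Cox regression to build an integrated radiomics-based model for PFS and OS prediction". Both endpoints are defined under Patient Treatment and Follow-up as times from initial diagnosis to an event.

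Under Model performance assessment: "The calibration plots and the Hosmer-Lemeshow test were used to compare the predicted and observed probabilities of the radiomics-based model". The Statistical analysis section adds only the software: "Hosmer-Lemeshow test, DCA and Kaplan-Meier survival analysis were performed using R software". No section gives a time point for these probabilities, a rule for a patient censored before it, the number of risk groups, the degrees of freedom, or a version of the test for censored data.

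Three statements fix the length of follow-up. Study population: "We retrospectively included patients with newly-diagnosed DLBCL between July 2013 and July 2019 in our institution". Patient Treatment and Follow-up: "Follow-up was performed every 3 months after the completion of treatment, and ended in July 2021". Patients are also excluded if they "underwent surgical resection, or had an incomplete follow-up"; incomplete is not defined.

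The section on feature selection says that LASSO "was applied to select the optimal features with non-zero coefficients in the training set", so some division of the cohort is implied, but it is not described.

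**The concern.** Hosmer-Lemeshow compares counts of events with predicted counts in groups of predicted risk, so each patient must be an event or a non-event at the chosen time. A patient diagnosed in July 2019 and event-free in July 2021 has no known status at 3, 4 or 5 years. Someone running the ordinary test at such a horizon must either leave that patient out or count the patient as event-free.

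Leaving such patients out removes only people who were event-free when last seen. The observed event proportion must then rise, whatever the shape of the hazard, and a well-calibrated model looks as if it under-predicts. Counting them as event-free pushes the observed proportion down whenever events continue after 2 years, which can hide a model that really does under-predict. Either way, the P value may reflect the coding and not the model.

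Excluding patients with incomplete follow-up does not clearly help. Read as loss to follow-up, it leaves the July 2021 cut-off untouched. Read as not followed to the horizon, it is itself a form of dropping.

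**Working it through.** **Inputs from the document.** Diagnosis July 2013 to July 2019; follow-up to July 2021; significance level 0.05. Potential follow-up is therefore 2021 - 2019 = 2 years at the shortest and 2021 - 2013 = 8 years at the longest. The plan states no sample size, event rate or calibration figure, so there is nothing of its own to reproduce.

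**Assumptions.** Accrual uniform, so potential follow-up is uniform on 2 to 8 years; n = 150 and 300; 5-year risk 26% or 50%; hazard constant, front-loaded (Weibull shape 0.7 or 0.5), or with all events by 2 years; normal linear predictor with SD 0.8; predictions equal to the true risks; 10 groups, 10 degrees of freedom; no loss before July 2021.

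**Step 1: potential follow-up shorter than the horizon t.** The share is (t - 2)/6: 0 at 2 years, 1/6 = 16.7% at 3, 2/6 = 33.3% at 4 and 3/6 = 50% at 5.

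**Step 2: status unknown.** This needs short potential follow-up and no event before the cut-off. If all events fall by 2 years, the share is (1 - risk) x (t - 2)/6:
- risk 50%: 0.50/6 = 8.3% at 3 years, 0.50 x 2/6 = 16.7% at 4, 0.50 x 3/6 = 25% at 5;
- risk 26%: 0.74/6 = 12.3%, 0.74 x 2/6 = 24.7%, 0.74 x 3/6 = 37%.

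With a constant hazard and 26% risk more patients are still event-free at their cut-off, and the shares reach about 14%, 28% and 40%. Over all scenarios: about 8-14%, 17-28% and 25-40%.

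**Step 3: observed 5-year event proportion.** If patients are dropped and all events fall by 2 years, it is risk/(1 - (1 - risk) x 0.5):
- true 26%: 0.26/(1 - 0.74 x 0.5) = 0.26/0.63 = 41.3%;
- true 50%: 0.50/(1 - 0.50 x 0.5) = 0.50/0.75 = 66.7%.

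With constant or front-loaded hazards, simulation gives 37.9-39.7% and 64.1-65.5%. Event-free coding gives 22.6-24.3% and 44.7-47.5%. The two codings agree with each other: for a constant hazard and 26% risk, 0.226/(1 - 0.40) = 37.7%, against 37.9% simulated.

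**Step 4: rejection of a perfectly calibrated model at 5 years** (simulation, nominal 5%).

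| Hazard | Dropped | Coded event-free |
|---|---|---|
| Constant | 28-65% | 5-27% |
| Front-loaded | 33-78% | 4-16% |
| All events by 2 years | 49-89% | same as complete data |

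Complete data give about 3-6%. Over all hazards, dropping gives about 14-47% at 4 years and 7-15% at 3 years. Event-free coding is close to nominal at 3 years. At 2 years the codings are identical.

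**Step 5: missed under-prediction.** For a hazard predicted 30% too low, at 5 years, complete data detect it in 35-78% of runs. Event-free coding detects it in 12-19% (constant) or 16-44% (front-loaded), with no loss if all events fall by 2 years.

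**Step 6: sensitivity to the assumptions, 5 years unless stated.**
- n = 60 to 100: dropping 10-37%, event-free coding 4-12%. Even complete data then detect the under-prediction in only 16-30%.
- Mostly early accrual: dropping 9-23%. Mostly late accrual: 80-100%.
- Cox model refitted in the same patients (8 degrees of freedom): dropping 38-99.8%, complete data 4.5-7.6%.
- Other settings (n = 100 to 250, 2-year event-free probability 0.6 to 0.9, linear-predictor SD 0.5 to 1.0, true or refitted model): dropping 8-44% at 4 years and 11-87% at 5. The mildest cases at n = 60 give about 5-8%.

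**Step 7: the replacement.** Under perfect calibration at 3 to 5 years, comparing mean predicted risk with 1-KM rejects in 2.5-4.6% of runs and the slope test in 4.5-6.0%. For the hazard predicted 30% too low, the first detects it in 33-92% at 5 years. In the data used to fit the model, it rejects in under 0.1% of runs, because agreement on average is then built in.

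**The case against.** The strongest reply is that the harm needs two things the documents do not state: a horizon beyond about 3 years, and the ordinary test with censored patients dropped. At 1 or 2 years there is no administrative censoring and the coding makes no difference. At 3 years dropping inflates the error only modestly, and event-free coding hardly at all. All of this stands. It makes the size conditional, but the plan neither commits to an early horizon nor rules out either coding.

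The size also moves with sample size and accrual pattern, and in the mildest small-sample cases it nearly vanishes. That stands too: excess rejection is not universal at 4 to 5 years.

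A reader might infer that censored patients were in fact dropped, so that any reported calibration P value is wrong. The text does not say so, and a method suited to censoring may have been used. A reader might also infer that Hosmer-Lemeshow is invalid for this model at any time. It is not: with complete status at 2 years or less it behaves properly.

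Finally, calibration is secondary. The objective is whether the signature adds to the IPI, no decision in the plan hangs on this P value, and calibration plots accompany it. That limits the weight of the point but does not remove it.

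**Conclusion.** The point holds as a conditional one. The plan applies a test that needs known status to a model for censored times and leaves open the horizon and the handling of censoring. Its own dates guarantee status only to about 2 years.

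Under the stated assumptions, dropping censored patients at 4 or 5 years raises the false rejection rate from about 3-6% to 14-47% and 28-89%. Event-free coding gives about 4-27% at 5 years, has no effect if all events fall by 2 years, and otherwise can conceal under-prediction. The direction under dropping follows from logic alone. The size rests on assumed sample size, risk, hazard shape and accrual, and is smaller with few patients or mostly early accrual and larger with mostly late accrual.

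This should be corrected, but it does not threaten the main conclusion about added value over the IPI. The calibration plots, time-dependent AUCs and bootstrap confidence intervals are not in question.

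**What to change.** In Model performance assessment, state the horizon or horizons for PFS and for OS. Replace the Hosmer-Lemeshow test with Kaplan-Meier-based calibration at those horizons: mean predicted risk against 1-KM, and the calibration slope, each with a confidence interval. Report these in patients not used to fit the model. If there are none, report a bootstrap optimism-corrected slope in the fitting data, since average agreement is uninformative there.

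Alternatively, keep the Hosmer-Lemeshow test but limit it to a horizon of 2 years or less, and confirm that every patient's status is known at that time.

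The cost is a change of wording and a little more analysis in R. Kaplan-Meier analysis and bootstrapping are already planned, and no new data are needed.

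### Calibration is checked by plots and a Hosmer-Lemeshow test, with no slope, observed/expected ratio or interval; at about 200 patients or fewer, a non-significant result does not exclude moderate miscalibration

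*Combined protocol and SAP*

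**What the plan says.** In the combined protocol and SAP, calibration is covered by one sentence under Model performance assessment: "The calibration plots and the Hosmer-Lemeshow test were used to compare the predicted and observed probabilities of the radiomics-based model". The only decision rule is the general one under Statistical analysis: "A two-sided *P* value of < 0.05 was considered statistically significant".

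Intervals are planned for discrimination: "The 95% confidence interval (CI) of the area under the curves (AUCs) were calculated by bootstrapping with 1000 resampling". Nothing comparable is planned for calibration: no slope, observed/expected ratio, confidence band or tolerance. The number of risk groups, the degrees of freedom and the horizon are not given either.

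The patients used for the calibration step are not named. A training set appears once, under Radiomics feature selection, where LASSO "was applied to select the optimal features with non-zero coefficients in the training set". The whole cohort is named only for the decision curve analysis. The split and its size are not described, and no total sample size or event count is given.

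**The concern.** The Hosmer-Lemeshow null hypothesis is that predicted and observed risks agree. Under a P<0.05 rule, the test can support the model only by failing to reject, and failing to reject becomes more likely as the sample shrinks. Without an estimate and an interval, a reader cannot tell a well-calibrated model from a sample too small to show that it is not.

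This matters here because the signature is selected from up to 1248 features (3 conventional and 1245 radiomic, before the ICC filter) and then passes through univariate screening and stepwise Cox regression. Models built in this way tend to give predictions that are too extreme in new patients, that is, a calibration slope below 1. The decision curve uses the same predicted probabilities, so a calibration error that goes unnoticed also affects the net-benefit statement.

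**Working it through.** **Inputs from the documents.** Two-sided alpha is 0.05. The models are Cox models for PFS and OS. Diagnoses run from July 2013 to July 2019 at one institution, and follow-up ended in July 2021, so the last patient has about 24 months of potential follow-up.

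**Inputs assumed, because the documents give none.** n = 100 to 500; mean risk at the horizon 20% or 30%; every patient's status known at the horizon; 10 risk groups. Known status keeps this check separate from the question of how the test handles censoring. The plan states no figure that could be reproduced first.

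**Set-up.** Predicted risk is 1 - exp(-H exp(z)), with z ~ N(0,1) and H chosen to give the mean risk. True risk uses slope 0.7 or 0.5 on z (H reset to keep the mean), or hazard multiplied by 1.5. The statistic is the sum over groups of (O - E)^2 / [E(1 - E/n_g)], referred to chi-square with 8 or 10 df. With a correct model it rejects in about 5-6% of samples (10 df) or 10-12% (8 df).

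**Size of the errors.** At mean risk 30%, the top-decile risk is predicted as 78%; it is truly 65% with slope 0.7 and 55% with slope 0.5. Hazard x1.5 means a mean risk predicted as 20% and truly 27%, or 30% and truly 39%.

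**Share of samples with P>=0.05** (8 df to 10 df, mean risk 20-30%; 1000 to 2000 replicates):

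| True error | n=100 | n=200 | n=300 |
|---|---|---|---|
| Slope 0.7 | 66-79% | 53-73% | 41-65% |
| Hazard x1.5 | 52-66% | 27-47% | not tabulated |
| Slope 0.5 | 38-58% | 14-39% | 7-25% |

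Repeat runs agreed to within about 2 percentage points.

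**Sensitivity to the assumptions.** With a logistic set-up and the true linear-predictor SD fixed at 1.2 (event rates 20-40%, 10 df), slope 0.7 is missed in 66-68% at n=100 and 54-56% at n=200. Slope 0.5 is missed in only 14-22% and 2-6%, because the predictions are then more widely spread. Overprediction by 0.5 on the logit scale is detected in 21-49% at n=200 and 76-94% at n=500. The miss rate therefore depends on n, on the spread of predictions and on the type of error.

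**Would an estimate with an interval do better?** For slope 0.7 at mean risk 20%, 95% CIs for slope and intercept flag the error in 46% at n=200, against 27-41% for the test, and in 63% against 37-51% at n=300. At n=100 there is little gain over the 8-df test: 32-34% flagged, against up to 100 - 66 = 34%. The main benefit is that the imprecision becomes visible. For a perfectly calibrated model, the slope CI half-width is 0.52-0.59 at n=100 and 0.22-0.25 at n=500. For overall observed risk at 30% and n=200, the half-width is 1.96 x sqrt(0.3 x 0.7/200) = 0.064, so observed/expected runs from about 0.236/0.30 = 0.79 to 0.364/0.30 = 1.21.

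**Patients used for fitting.** Refitting by maximum likelihood makes the apparent slope 1 by construction, so neither an in-sample slope nor the in-sample test can show overfitting. One illustration, with 80 replicates in each of two scenarios, used logistic LASSO, 150 patients and 400 correlated features. The apparent test passed 91-93% of models whose median true slope in new patients was 0.33-0.43. It is not a Cox model and its inputs are assumed, so it shows the direction of the problem and not its size in this study.

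**The case against.** Three stronger readings are tempting, and the documents support none of them.

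- A reader might infer that calibration rests on a P value alone. It does not: calibration plots are planned, and plots show the size and direction of error. They have no stated confidence bands, however, so they do not show how much of a deviation is noise.
- A reader might infer that non-significance will be reported as agreement. No sentence says so, and the P<0.05 rule is a general significance statement. What stands is that the plan neither rules this reading out nor offers another numerical summary.
- A reader might infer that the test misses relevant miscalibration in most samples of single-centre size. That cannot be shown. The documents give no sample size, event count or definition of relevant error, and several settings above are missed in under half of samples at n=200.

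It is also fair to say that in-sample optimism argues for separate validation more than against this particular test, since an apparent slope would fail in the same way. Mention of a training set suggests that a split exists, although its use for calibration is unstated. Finally, the stated objective is whether the signature improves on the IPI. Calibration is supportive, and changing its summary does not change the probabilities that enter the decision curve. These points limit the weight of the concern but do not remove the gap.

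**Conclusion.** The point holds in a conditional form. Calibration is assessed by plots and a test, without slope, observed/expected ratio or interval, in patients who are not named. If n is about 200 or less, a non-significant result does not exclude moderate miscalibration: a true slope of 0.7 is missed in about two-thirds to four-fifths of samples at n=100 and about half to three-quarters at n=200. Under the same conditions, slope 0.5 or a hazard understated by a factor of 1.5 is detected in more than half of samples at n=200.

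These figures rest on the assumed mean risk, spread, grouping and known status, and on predictions treated as fixed. The absence of an interval and of a named data set rests on the text alone. This is a cheap improvement to a supportive analysis. It is not a flaw that overturns the comparison with the IPI.

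**What to change.** State in the SAP that Hosmer-Lemeshow P>=0.05 will not be used as evidence of agreement. For PFS and OS, at each stated horizon:

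- Report the calibration slope and the observed/expected risk, each with a 95% CI, taking observed risk from Kaplan-Meier.
- Draw the calibration plots with confidence bands.
- Compute all of these in patients not used to fit the signature or the integrated model. Otherwise, give bootstrap optimism-corrected values that repeat the whole model-building process (LASSO, univariate screening and stepwise selection). Name the data set.
- Interpret calibration from the estimates and the width of their intervals.

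A fixed pass rule, such as a slope CI lying inside 0.8 to 1.2, should not be added. It needs a half-width of at most 0.20, and under the main assumptions a perfectly calibrated model never met it at n=100 to 500, so it could not separate good models from poor ones.

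The cost is SAP wording and a few lines of R on data already collected. The downside is a less favourable and more uncertain calibration statement.

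### Decision-curve net benefit is computed in the whole cohort, which includes the patients who trained the radiomics signature, with no optimism correction, so it is inflated on average

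*Combined protocol and SAP*

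**What the plan says.** Radiomics feature selection, on the LASSO Cox step: "algorithm with 10-fold cross-validation was applied to select the optimal features with non-zero coefficients in the training set". It continues: "The radiomics signature was developed by linear combination of the selected features weighted by their respective coefficients". Two further steps use outcomes, and the plan does not say in which patients they are run. One is the cut-off: "The cut-off value of the radiomics signature was identified by X-tile software". The other, in Model construction, is the integrated model: "all significant variables were enrolled into a stepwise multivariate Cox regression", after univariate screening.

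Model performance assessment then states that decision curve analysis "was applied to determine the clinical utility" by "quantifying the net benefits under different threshold probabilities in the whole cohort". It is the only analysis in that section with a named data set. The resampling described there has a different purpose: "The 95% confidence interval (CI) of the area under the curves (AUCs) were calculated by bootstrapping with 1000 resampling".

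Study population describes one retrospective single-institution cohort. No external cohort is named.

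**The concern.** A model scored on the patients who built it looks better than it will in new patients. Here the signature is drawn from up to 1,248 candidate features (before the ICC filter), so there is ample room for overfitting. The two resampling procedures in the plan do not address this. The 10-fold cross-validation belongs to LASSO selection, and the 1,000 bootstrap samples give AUC confidence intervals, which describe sampling uncertainty and not optimism.

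The decision-curve sentence names no comparator, but the objective is to find out whether the signature adds to the IPI. The IPI is a fixed score, so its own curve is hardly inflated and the bias falls almost wholly on one side of the comparison. Decision curve analysis is the only method the plan assigns to clinical utility. The conclusion at stake is therefore whether use of the signature would improve decisions at all, and not only by how much.

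**Working it through.** The plan gives no net-benefit figure, sample size or event count, so there is nothing to reproduce. The check is one identity plus simulation under stated assumptions.

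**Formula.** At threshold t, net benefit is NB = TP/n − (FP/n) × t/(1 − t). At t = 0.30 the weight on false positives is 0.30/0.70 = 0.43. If w is the training share and every patient's status at the horizon is known, then

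NB(whole) = w × NB(training) + (1 − w) × NB(non-training).

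If all modelling is locked in the training set, the non-training term is unbiased and the expected inflation is w × [NB(training) − NB(true)].

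**Worked example** (simulation with N=150, w = 2/3, pure-noise signature, 3 years, t = 0.40). Mean NB was 0.059 in the whole cohort, 0.027 in the held-out third and 0.022 in new patients. The implied training value is (0.059 − 0.027/3)/(2/3) = 0.050/0.667 = 0.075. The inflation is 0.059 − 0.022 = 0.037.

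**Limit of the identity.** Diagnosis ran from July 2013 to July 2019 and follow-up ended in July 2021, so potential follow-up is 2 to 8 years. Status at a later horizon would be censored for some patients. The plan states no horizon and excludes patients who "underwent surgical resection, or had an incomplete follow-up" without defining the last term. The exact weighting is therefore not established, but the direction of bias does not depend on it.

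**Main simulation: assumptions.**
- 200 or 600 retained features in 20 correlated blocks (loading 0.8), three blocks correlated 0.5 with the latent IPI.
- IPI scored 0–5 with log-HR 0.6 per SD; five other clinical variables without independent effect.
- One independent prognostic block with log-HR 0 (nil), 0.3 (weak) or 0.6 (strong).
- Two-year event rate 34–37%; censoring uniform over 2–8 years.
- Pipeline in training patients: Cox LASSO with 10-fold CV, continuous score or maximum-log-rank cut-off, univariate P<0.05, backward AIC.
- Gain = NB(radiomics-based model) − NB(Cox model with IPI alone). Truth = the locked model in 20,000 new patients. Inflation = whole-cohort gain − true gain.
- 200 runs per scenario at a 67% training share.

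**Mean inflation of the gain over the IPI, t = 0.30:**

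| | N=150 | N=300 | N=600 |
|---|---|---|---|
| Minimum-CV penalty, 2 years | 0.032–0.047 | 0.020–0.032 | 0.011–0.021 |
| One-SE penalty, 2 years | 0.006–0.016 | 0.003–0.012 | 0.002–0.012 |
| Minimum-CV, 3 years, censored (Kaplan-Meier NB) | 0.027–0.044 | 0.014–0.032 | 0.007–0.019 |
| IPI model's own inflation | 0.006 | 0.003 | 0.001 |

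An inflation of 0.032 is 3.2 net true positives per 100 patients. With training shares of 50% and 80% (minimum-CV) it was 0.029–0.046 at N=150 and 0.019–0.035 at N=300. At t = 0.30 the mean was positive in all 104 scenario-by-pipeline combinations, by at least 3.9 Monte Carlo SE. Over thresholds 0.10–0.50 the means ran from 0.000 to 0.070.

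**Whole-cohort gain against true gain (minimum-CV, continuous score, t = 0.30):**

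| | N=150 | N=300 | N=600 |
|---|---|---|---|
| Nil | +0.011 to +0.012 vs −0.021 to −0.025 | +0.007 vs −0.013 to −0.016 | +0.003 to +0.005 vs −0.008 to −0.009 |
| Strong | +0.038 to +0.044 vs +0.001 to +0.003 | +0.039 to +0.043 vs +0.013 to +0.016 | +0.033 to +0.038 vs +0.019 |

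In all 24 nil or weak settings with the continuous score (12 per penalty rule), the mean whole-cohort gain was positive and the mean true gain negative.

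**Share of all runs with whole-cohort gain above 0 but true gain not above 0:**
- Nil or weak, minimum-CV, continuous score: 54–76%, against 20–36% for the same models assessed in non-training patients.
- Nil or weak, one-SE, continuous score: 17–39%.
- Strong, continuous score: 28–42%, 6–11% and 0–0.5% at N=150, 300 and 600.
- Strong, dichotomised group: 51–60%, 23–40% and 10–14%. The plan does not say whether the score or the group enters the Cox model.

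**Second simulation, different design** (1,248 features, 3 years, N=100, 150 and 250, two-thirds training, 200 runs per scenario; no cut-off, screening or stepwise step). Net benefit was inflated by 0.022–0.061 at thresholds 0.3–0.5, 0.015–0.042 at 0.2 and 0.000–0.021 at 0.1. With a noise signature the gain over an IPI-like score at 0.3–0.5 was +0.009 to +0.027 in the whole cohort, against −0.025 to −0.008 in new patients.

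**Signature alone.** With no clinical-variable selection (40 runs per setting, minimum-CV, t = 0.30), whole-cohort and true gains were +0.014 vs −0.012 (N=150, nil), +0.010 vs −0.014 (N=300, nil) and +0.044 vs +0.002 (N=150, strong). The inflation is thus 0.026, 0.024 and 0.042 without any contribution from the other clinical variables.

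**The case against.** The strongest case concerns weight, not direction. The objective is prognostic value, which the Cox models, time-dependent AUCs and Delong's test address. The decision curve is one descriptive sentence, is not designated primary and carries no test. Its comparator is inferred. The size rests wholly on assumed inputs and ranges from 0.002 to 0.047 at t = 0.30 for a 67% training share at 2 years. The bias can vanish at low thresholds, where nearly everyone is classed as high risk. Part of the wrong-sign share is not due to the whole-cohort choice, since the same models gave 20–36% in non-training patients. Cross-validation also assesses the modelling procedure and not the one locked training-set signature.

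Much of this stands as a limit on what can be claimed: the size is unknown, a single data set can differ from the average, and the point touches the clinical-utility conclusion and not every prognostic result. It does not remove the bias. No analysis is designated primary, and this is the only one that supports a utility claim. LASSO shrinkage reduces the inflation without eliminating it. The suggestion that selection of clinical variables produced the effect fails, because the inflation persists without them. The objection to cross-validation also carries little weight. Judged against the locked training-set model in the same three 40-run settings, the cross-validated curve had RMSE 0.028, 0.027 and 0.046, against 0.044, 0.035 and 0.060 uncorrected.

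**Conclusion.** The concern holds. The plan states that the decision curve uses a cohort containing the training patients and describes no correction, so net benefit of the radiomics-based model, and its gain over the IPI, are overstated on average. Confidence is high for the direction only. The size for this study cannot be derived, and the figures above are illustrative. They shrink with N, are smaller under the one-SE penalty and can be negligible at low thresholds. Where true added value is nil or weak, the average apparent gain has the wrong sign. Where it is strong, the gain is overstated, and the sign may also be wrong in a small cohort or if the dichotomised group is used. The analysis should be corrected before any statement on clinical utility is made.

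**What to change.** Replace the last sentence of Model performance assessment with text such as:

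> Decision curve analysis quantified net benefit at a stated time horizon, over a stated range of threshold probabilities, for the radiomics-based model, the IPI alone, treat-all and treat-none. Predictions in the whole cohort were cross-validated: LASSO, cut-off, univariate screening and stepwise Cox were repeated in each of 10 folds, and each patient was scored only by a model built without that patient. The uncorrected whole-cohort curve is labelled apparent performance.

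The ICC filter does not use outcomes and need not be repeated. The same rule should apply to the AUC comparison and calibration if they are run in data that include training patients.

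**Check of the fix** (600 features, N=150 and 300, minimum-CV, t = 0.30, models built from the whole cohort). The uncorrected gain differed from truth by +0.028 to +0.052, the cross-validated gain by −0.010 to +0.001, which is slightly conservative. RMSE was 0.030–0.039 against 0.057–0.072 at N=150, and 0.017–0.022 against 0.036–0.046 at N=300. Cross-validation was not checked with the one-SE penalty.

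**Alternatives.** Bootstrap optimism correction that repeats all outcome-using steps is acceptable, though not simulated here. A curve in non-training patients only is unbiased if every step was locked in the training set, and it assesses the signature actually built, but it is less precise. At N=150 and a 67% share its RMSE was 0.041–0.054 against 0.049–0.060 uncorrected with minimum-CV, but 0.024–0.038 against 0.016–0.032 with one-SE. If the cut-off or stepwise model used the whole cohort, this option does not suffice.

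**Cost.** No new data are needed. There are 10 extra pipeline fits per endpoint, so 2 × 10 = 20 for PFS and OS. If the cut-off enters the model, the X-tile step must be re-implemented in code, because X-tile is separate software. The net benefit shown will probably be less favourable.
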